---

## PROTOCOL SUMMARY

Study Number and Title:
 
PP PLR 03: A Randomized, Controlled, Parallel, Multicenter Study Assessing Perfusion Outcomes with PINPOINT® Near Infrared Fluorescence Imaging in Low Anterior Resection (PILLAR III).

Clinical Phase: Pivotal Study/Non Significant Risk Medical Device

Study Objectives:
 
Primary:
 

• To demonstrate an improvement in post-operative anastomotic leak rate in low anterior resection procedures where colon and rectal tissue perfusion is evaluated using PINPOINT® endoscopic fluorescence imaging or SPY Elite® Intraoperative Imaging as an adjunct to standard surgical practice compared to surgical procedures performed according to standard surgical practice alone.

 
Secondary:
 

• To evaluate the ability of the PINPOINT system or SPY Elite system to provide sufficient visualization for assessment of blood flow and related tissue perfusion during the procedure.

• To evaluate the effectiveness of assessing perfusion of colon and rectal tissue using PINPOINT or SPY Elite in reducing the rate of post-operative abscess requiring surgical management.


Study Design
 
This is a randomized, controlled, parallel, multicenter study to determine the reduction in post-operative anastomotic leak rate in low anterior resection (LAR) procedures where colon and rectal tissue perfusion is evaluated using PINPOINT or SPY Elite as an adjunct to standard surgical practice compared to surgical procedures performed according to standard surgical practice alone. The study is a two-stage adaptive design that allows a mid-trial reassessment of sample size. Therefore, a minimum of 450 and a maximum of 1000 subjects will be enrolled at up to 40 centers in North America. Prior to enrolling study subjects, participating surgeons at each center will be trained to perform perfusion assessment with PINPOINT.
 
Screening:
 
Patients scheduled for an open, or minimally invasive low anterior resection for a rectal or rectosigmoid neoplasm with curative intent with a planned anastomosis located 10 cm or less from the anal verge will be evaluated at baseline to determine if they meet the inclusion/exclusion criteria of the protocol. Subjects will be assessed to determine overall health status, including demographics, vital signs and predictive factors that may influence surgical outcomes. Eligible patients who provide informed consent will be considered for inclusion into the study.
 
Day 0:
 
During anesthesia, subjects will be randomized (1:1) to either the PERFUSION (PFN) Arm or the STANDARD (STD) Arm. Subjects in each arm will be randomized according to an independently generated randomization scheme to receive either perfusion assessment with PINPOINT and/or SPY Elite during the surgical procedure or to receive the standard of care procedure. Randomization will be stratified by site and by whether or not the patient received prior neoadjuvant therapy.
 
Subjects in the PFN Arm will undergo a LAR according to the surgeon's standard practice with the addition of intraoperative imaging using PINPOINT and/or SPY Elite NIR fluorescence imaging to assess colon and rectal tissue perfusion during the following steps of the procedure:

- perfusion of proximal transection margin after IMA ligation; prior to bowel transection
- perfusion of the mucosal aspect of the completed anastomosis (with the exception of hand sewn coloanal anastomoses which will involve assessment of the mucosal aspect of the proximal colon only)

Subjects in the PFN Arm may also undergo additional or repeat intraoperative imaging using PINPOINT and/or SPY Elite NIR fluorescence imaging based on the surgeon's clinical judgment.

Subjects in the STD Arm will undergo a LAR according to the surgeon's standard practice only.

All subjects will receive the hospital/institution and surgeon's standard pre-operative, post-operative and post discharge care with the addition of any study specific requirements. An air leak test on all anastomoses (with the exception of hand sewn coloanal anastomosis when applicable) will be performed in the surgeon's standard fashion.

Details of the actual surgical technique will be documented post-operatively. The surgeon's ability to sufficiently assess blood flow and related tissue perfusion using PINPOINT or SPY Elite will be recorded. The final height of the anastomosis from the anal verge will be determined by assessing the markings on the stapler or by rigid proctoscopy, at the discretion of the surgeon. The site of the proximal anastomosis segment and the level of the inferior mesenteric artery and vein ligation will also be recorded.

*Follow-up and Post-operative Complications:*

All subjects will be followed to monitor occurrence of post-operative complications up to Week 8 post-surgery ( $\pm 14d$ ). All subjects will have study specific follow-up visits on Day 1, date of discharge, Week 8 and the date of ileostomy closure (if applicable). Subjects with a discharge date later than Week 8 who did not have an ileostomy, will be followed until the Week 8 visit. All subjects with a diverting ileostomy must have flexible sigmoidoscopy or proctoscopy and/or contrast enema to evaluate the anastomosis between 3 weeks postoperatively and the Week 8 visit ( $\pm 14d$ ).

Subjects who present with a clinical suspicion of anastomotic leak during the study who do not require urgent reoperation will have a CT scan with PO and, if diverted or if necessary, rectal contrast to confirm. A leak is considered confirmed if any evidence of endoluminal contents (air, fluid, GI contents or contrast material) through the anastomosis is identified by imaging, drain output or at reoperation, or by endoscopic evidence of an anastomotic defect. All scans will be reviewed by an independent radiologist for confirmation. The presence of infection or abscess thought to be related to the anastomosis may be classified as an anastomotic leak at the surgeon's discretion even if it cannot be definitively identified as visualized during an operation or by contrast extravasation. All anastomotic leaks will be followed until resolution.

All adverse events and post-operative complications occurring during the study period will be reported and graded according to the Clavien-Dindo system (Table 2).

Analysis of anastomotic leak rate will be based on the occurrence of a leak according to the protocol definition at any time during the study up to Week 8 ( $\pm 14d$ ).

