Minimally invasive and open LAR procedures are both considered to be oncologically safe for the patient. Data indicates that the oncologic outcomes between minimally invasive and open resections for treatment of primary rectal cancer are the same. A recent retrospective comparative study has shown that there is no significant difference in the 5 year local recurrence rate and cancer free survival rate between laparoscopic and open surgery.

There are a number of complications that can occur after LAR, with anastomotic complications being the most serious. Anastomotic bleeding, leaks, strictures, and fistulas are complications that may be related to surgical technical factors such as tension, stapler malfunction and tissue ischemia; or to patient related factors such as male sex, local sepsis, poor nutrition, immunosuppression, morbid obesity and/or radiation exposure. Anastomotic leak is considered the most dreaded of complications and is reported to occur 3-20% of the time in colorectal surgery and the risk increases for lower anastomoses. Anastomoses below 10 centimeters

(cm) from the anal verge have been shown to be a specific predictor of leak in a prospective study. Another recent prospective randomized study in patients undergoing a colorectal resection (LAR, proctocolectomy, or Hartmann's reversal, with low colorectal or coloanal anastomosis or ileoanal pouch anal anastomosis [IPAA] procedures) with planned anastomosis  $\leq 10$  cm from the anal verge demonstrated an overall leak rate of 12%.

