### 10.3 Statistical Analysis

Analysis of these hypotheses will be conducted using a z-test (i.e., normal approximation to the binomial distribution, using a pooled variance estimate and without continuity correction), using a (one-sided) significance level of 0.025.

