### 10.4 Adaptive Design and Sample Size Considerations

Available literature does not provide a precise estimate of the expected anastomotic leak rate in the control group or in the treatment group. As previously described, anastomotic leak is reported to occur in a wide range of 3-20% of the time in colorectal surgery and the risk increases for lower anastomoses. In the limited prior experience with the PINPOINT PILLAR II study (n=139 subjects) the anastomotic leak rate was 1.4%.

Given the limited knowledge of control incidence and the treatment effect size, the PILLAR III study will employ an adaptive design with a mid-trial sample size re-assessment. The planned sample size is  $N = 800$ , with possible early stopping for efficacy or futility at an interim analysis at  $N = 450$ . The planned total of 800 subjects will provide >80% power to test the one-sided hypothesis of superiority for treatment over control in leak rate at the 0.025 significance level if the true leak rates  $p_c$  and  $p_t$  are 12.5% and 6.25% (a 50% relative reduction), assuming a two-look group sequential analysis plan (with Pocock alpha-spending bounds and analyses at 450 and 800). If the trial does not stop at  $N = 450$ , sample size will be assessed at that time and possibly increased up to a maximum of 1000 subjects, using the method of Chen et al. and described in Mehta and Pocock.

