3.2 Visit Schedule and Visit Windows

Baseline/Screening Procedures (Day -30 to Day 0)

After signing the informed consent form, subjects will be assigned a screening and be evaluated for eligibility into the study.

The following procedures will be conducted during the baseline assessment:

	Forms			
	Title	Statistical Analysis Plan Template		
	Code	Version	Effective Date	Page
	FRM_ST03_032	01	23 Apr 2015	8 of 20

- Collection of demographics, surgical risk factors, pre-operative diagnosis.
- Vital signs (heart rate and blood pressure), height and weight.
- Serum tests (bilirubin, sodium, creatinine and INR) for MELD Score.
- Pregnancy test (urine test or institution standard of care) for females of childbearing potential.

Day 0 Procedures

On Day 0, the following will be completed before randomization and surgery:

- Serum hemoglobin, prealbumin, and albumin measurement.

During anesthesia, subjects will be randomized. Subjects are considered enrolled upon randomization.

According to the randomization assignment, subjects in the PERFUSION arm will receive perfusion assessment with PINPOINT and/or SPY Elite during surgery and undergo surgery according to the surgeon's standard practice. Subjects randomized to the Standard arm will undergo the surgery according to the surgeon's standard practice only. All subjects will receive the hospital/institution and surgeon's standard pre-operative and post-operative care with the addition of any study specific requirements.

An intra-operative measurement of hemoglobin should be performed at the time of anastomosis if the subject experiences a hypotensive event requiring intraoperative management (e.g. use of vasopressors) or blood loss greater than 500 ml at the time of anastomosis.

Post-operative Follow-up Visits (Day 1 to Last Study Visit)

Subjects will have standard of care assessments throughout the study according to the hospital/institutions standard procedures as well as study specific visits on postoperative Day 1, the date of discharge, Week 8 (56 ±14 days) and the date of ileostomy closure, if applicable. Subjects will be assessed for the following throughout the study:

- Serum hemoglobin measurement (Day 1).
- Evidence of anastomotic leak.
- Assessment and grading of post-operative complications.
- Concomitant medications and procedures.
- Adverse events/adverse device effects.

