5.4 Demographics and baseline characteristics

The demographic and baseline characteristics will be summarised by treatment arm and overall by means of descriptive statistics.

The following demographic characteristics will be provided for the randomized patients:

- Age, gender, race, surgical risk factors, pre-operative diagnosis.
- Vital signs (heart rate and blood pressure), height and weight.
- Serum tests (total bilirubin, creatinine, serum sodium and INR) for MELD Score.
- Pregnancy test (urine test or institution standard of care) for females of childbearing potential.

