6.1 Analysis of primary endpoint

The primary objective is to demonstrate an improvement in post-operative anastomotic leak rate in low anterior resection procedures where colon and rectal tissue perfusion is evaluated using PINPOINT or SPY Elite near infrared fluorescence imaging as an adjunct to standard surgical practice compared to surgical procedures performed according to standard surgical practice alone.

$$H_0: p_t = p_c$$

$$H_1: p_t < p_c$$

Where p_t and p_c represent the expected population incidences of post-operative anastomotic leaks in the treatment (PERFUSION) and control groups, respectively. Within their respective treatment groups, p_t and p_c will be estimated as the number of subjects who experience a post-operative anastomotic leak divided by the number of subjects who either are included in the numerator or are known to be free of such leaks as of the 8 weeks visit. Subjects without a known anastomotic leak but with less than 6 weeks of follow-up (i.e., insufficient follow-up to declare them "leak-free") will not be included in these estimates.

Analysis of these hypotheses will be conducted using a z-test (i.e., normal approximation to the binomial distribution, using a pooled variance estimate and without continuity correction), using a (one-sided) significance level of 0.025.

A secondary analysis of the primary endpoint will be carried out on the As-treated population as well as on the PP population.

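### The primary leak comparison is unadjusted although sex, body size and albumin are recorded before randomization: a valid test that gives up a little precision

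*Protocol*

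**What the plan says.** On screening, the Protocol Summary states: "Subjects will be assessed to determine overall health status, including demographics, vital signs and predictive factors that may influence surgical outcomes". Protocol 1.1 lists technical causes of anastomotic complications and then "patient related factors such as male sex, local sepsis, poor nutrition, immunosuppression, morbid obesity and/or radiation exposure". The list covers bleeding, leaks, strictures and fistulas together.

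Protocol 8.2 collects demographics, surgical risk factors, height and weight at baseline. On Day 0, before randomization and surgery, Protocol 8.3 and SAP 3.2 require "Serum hemoglobin, prealbumin, and albumin measurement". Prior neoadjuvant therapy is known at that point because it is a randomization stratum within site (Protocol 5.1, SAP 3.4).

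The primary test in SAP 6.1, as in Protocol 10.3, is a "z-test (i.e., normal approximation to the binomial distribution, using a pooled variance estimate and without continuity correction", at one-sided 0.025. The as-treated and per-protocol analyses change the population but not the method. For baseline data, SAP 5.4 says: "The demographic and baseline characteristics will be summarised by treatment arm and overall by means of descriptive statistics". The list that follows there does not include albumin or prealbumin. The only regression on leak is the poolability model in SAP 4.3, which contains treatment, center and their interaction.

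**The concern.** Stratification balances site and neoadjuvant therapy only. Sex, body size and nutritional state are left to chance, and with an unadjusted test any chance imbalance in them passes straight into the estimated leak difference. A pre-specified adjusted analysis would remove that part of the noise from data the trial already holds, while the target stays the marginal risk difference.

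At stake are a small amount of power and protection against an awkward result. If the arms turn out unbalanced on a recognised risk factor, an adjusted estimate produced afterwards would be post hoc in a trial labelled pivotal.

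**Working it through.** **Inputs from the documents.** Leak rates pc = 0.125 and pt = 0.0625; looks at 450 and 800 with Pocock alpha spending; one-sided 0.025; 1:1 allocation; stated power 81.6% (Protocol 10.4 and the sample size rationale that follows it).

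**Inputs assumed.** Three independent binary predictors: male sex, obesity and low albumin, present in 60%, 30% and 15% of subjects, with odds ratios from 1.5 to 2.5. The documents give no odds ratios. For prevalence, Protocol 1.2 reports 53% male and 30% with BMI above 30 in PILLAR II, and no figure for low albumin.

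**Step 1: reproduce the protocol's power.**
- Interim alpha: 0.025 × ln[1 + (e − 1) × 450/800] = 0.0169, z = 2.122. This matches the stated threshold.
- Final bound from the bivariate normal with correlation √(450/800): z = 2.220.
- Pooled rate 0.09375; 2 × 0.09375 × 0.90625 = 0.1699.
- Expected z: 0.0625/√(0.1699/225) = 2.274 at the interim and 0.0625/√(0.1699/400) = 3.032 at the end.
- Probability of crossing either bound: 81.6%, as stated.

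**Step 2: variance with and without adjustment.** Let mc and mt be a subject's leak risk under control and under perfusion imaging given the predictors, with intercepts set so that their averages are 0.125 and 0.0625. Per subject:
- unadjusted: 2[pc(1 − pc) + pt(1 − pt)] = 2(0.1094 + 0.0586) = 0.3359
- standardised: E[2mc(1 − mc) + 2mt(1 − mt)] + Var(mc − mt)

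The ratio of the two multiplies the variance in Step 1. The equivalent unadjusted N is 800 divided by the ratio.

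| Assumed odds ratios (sex / obesity / albumin) | Adjusted variance | Ratio | Power | Equivalent N |
|---|---|---|---|---|
| none (z-test) | 0.3359 | 1 | 81.6% | 800 |
| 1.5 / 1.5 / 1.5 | 0.3331 | 0.991 | 81.9% | 807 |
| 2 / 1.5 / 2 | 0.3296 | 0.981 | 82.4% | 815 |
| 2.5 / 2 / 2.5 | 0.3232 | 0.962 | 83.1% | 832 |

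Using 53% male instead of 60% moves power by less than 0.1 point in each row.

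**Step 3: cross-check by another route.** Replace the three predictors by one risk score with an assumed C-statistic. At 0.60, 0.65 and 0.70 the variance falls by 1.1%, 2.7% and 5.1%, and power is 82.1%, 82.7% and 83.6%. The order of magnitude is the same.

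**Step 4: size of chance imbalance.** In the middle row, the variance due to imbalance in the three factors is (0.3359 − 0.3296)/N. At N = 450 that is 0.0063/450 = 0.000014, a standard deviation of about 0.37 points and a 95% range of about ±0.7 points, against a planned difference of 6.25 points.

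**Step 5: the SAP's own sample size.** SAP 3.3 takes everyone enrolled through 31 March 2017, with no calculation, and SAP 6.1 describes no interim look. Single-look power is Φ[(0.0625 − 1.96 × pooled SE)/unpooled SE]. At an assumed N of 400 this is (0.0625 − 1.96 × 0.02915)/0.02898 = 0.185, or 57.4%. With 2% less variance it is 58.2%. At 200 and 600 the figures are 32.8% to 33.3% and 74.9% to 75.7%.

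**The case against.** The strongest reply is that the gain is trivial. In the middle case it is 0.8 points, no more than the spread among ways of computing the same unadjusted power: 81.6% pooled, 82.1% unpooled, 82.6% by exact binomial simulation. That stands as a statement of size. It does not remove the point, because the precision is real and needs no further data.

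It is also fair that the protocol uses prognostic or baseline factors elsewhere: in the comparison of subjects with and without data (Protocol 10.8) and in poolability testing (Protocol 10.9). Neither enters the treatment comparison. Protocol 1.1 does not give a leak-specific list, and it says morbid obesity, which is narrower than the BMI above 30 category whose 30% prevalence is used here.

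Three stronger readings are tempting, and the documents do not support them:

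- **That the unadjusted test is biased or inflates type I error.** It is a valid comparison of randomized arms.
- **That the gain reaches about 83.8% power, or nearly 50 subjects.** That takes a fourth strong predictor, planned anastomosis height. The documents show it as an eligibility limit of 10 cm and do not show that the value is recorded. Nor can it be added prospectively: the SAP's enrollment cut-off is 31 March 2017 and its final version is dated 10 April 2017.
- **That adjustment would make up for a small enrolment.** Step 5 shows that it would not.

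**Conclusion.** The point holds as a modest, nearly free improvement and not as a validity defect. For the three predictors the trial can be shown to collect, the variance reduction is about 1 to 4%. In the protocol's 450/800 design that is 81.6% power rising to about 81.9 to 83.1%, or about 7 to 32 subjects of 800. Under the SAP's date-based sample size a similar proportional reduction would apply, but the power itself cannot be stated because N is not given.

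These figures rest on assumed odds ratios, independent predictors and an assumed 15% with low albumin. The PILLAR II prevalences come from a different case mix (44% diverticulitis, 25% rectal cancer), so they are only a guide.

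**What to change.** Before leak outcomes are seen by arm, amend SAP 6.1 and Protocol 10.3 as follows:

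- Estimate the risk difference by standardisation (g-computation) from a logistic model with arm, prior neoadjuvant therapy, sex, BMI and pre-operative albumin. Neoadjuvant therapy belongs in the model because it is a stratification factor.
- Use a robust or delta-method variance and keep the one-sided 0.025 level.
- Fill missing baseline values with the overall mean, taken across both arms.
- Keep the unadjusted z-test as the sensitivity analysis.
- If the interim look is retained, use the same adjusted statistic at both looks and in the conditional-power rule of Protocol 10.4.
- Do not adjust for final anastomosis height or diversion. Both are settled after the assignment is disclosed, and Protocol 8.3.2.3 ties diversion to the perfusion assessment.

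The cost is SAP wording and a little more analysis work; no new data are needed. The one real downside is that type I error control for the adjusted estimate is a large-sample property. At the planned rates, 800 subjects give 400 × 0.125 + 400 × 0.0625 = 75 leaks for five coefficients, and half that number of subjects gives half the leaks. The covariate list should therefore stay this short.

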**Study Population:**

The study will enroll a minimum of 450 and maximum of 1000 subjects scheduled to undergo an open or minimally invasive LAR. To be eligible for the study, subjects must meet the following main inclusion criteria:

- 18 years of age and older.
- Undergoing open, or minimally invasive LAR for the treatment of rectal or rectosigmoid neoplasms.
  - Subjects with rectal or rectosigmoid neoplasm(s) may be treated with or without neoadjuvant therapy. Long-course neoadjuvant therapy must have been completed  $\geq 6$  weeks prior to LAR surgery (Day 0).
- Have a planned low circular stapled or transanally hand sewn anastomosis  $\leq 10$  cm from the anal verge, with or without reservoir/pouch.

Subjects meeting any of the following criteria will be *excluded* from the study:

- Undergoing stapled anastomosis with the use of an experimental or non-FDA approved stapler.
- Undergoing ileoanal reconstruction, proctocolectomy, abdominoperineal resection, Hartmann's procedure, Hartmann's reversal or multiple synchronous colon resections (e.g., LAR and concomitant right colectomy).
- Subject has received and completed a course of pelvic radiotherapy  $\geq 6$  months prior to LAR surgery (Day 0).
- Subject has previously undergone a leftsided colon resection.
- Subject has previously undergone a rectal resection.
- Subject has recurrent rectal or rectosigmoid cancer.
- Has a diagnosis of locally advanced rectal or rectosigmoid cancer undergoing extended en bloc operations.
- Has a diagnosis of Stage IV rectal or rectosigmoid cancer with any multifocal metastases or single site metastasis with tumor size of  $> 2$  cm.
  - a. Intra operative incidental finding or preoperative suspicion of Stage IV cancer with isolated (single site) metastasis ( $\leq 2$  cm) or limited metastases ( $\leq 3$ ), with largest lesion  $\leq 2$  cm in size, does not exclude the subject.
- Diagnosis of inflammatory bowel disease. Hepatic dysfunction defined as MELD Score  $> 12$ .
- Renal dysfunction with serum creatinine  $\geq 2.0$  mg/dL.
- Known allergy or history of adverse reaction to ICG, iodine or iodine dyes.
- Pregnant or lactating female.

